### 2.1.3.12 Last contact date

The last contact date will be derived for subjects not known to have died at the analysis cut-off using the last complete date among the following:

**Table 2-2 Last contact date data sources**

Source data	Conditions
Date of Randomization	No condition
Start/End dates from further antineoplastic therapy	Non-missing medication/procedure term.
Start/End dates from drug administration record	Non-missing dose. Doses of 0 are allowed.

Source data	Conditions
End of treatment date from end of treatment page	No condition
Safety follow-up visit date	If the visit is completed and the patient doesn't die before the visit
Surgery date from surgery page	"Was a Surgery Performed?" marked as 'Yes'
Laboratory/PK collection dates	Sample collection marked as 'done'.
Vital signs date	At least one non-missing parameter value
Performance Status date	Non-missing performance status
Start/End dates of AE	Non-missing verbatim term
Imaging assessment date	Imaging marked as done

The last contact date is defined as the latest complete date from the above list on or before the data cut-off date. The cut-off date will not be used for last contact date, unless the subject was seen or contacted on that date. No date post cut-off date will be used. Imputed dates (e.g. the analysis cut-off date programmatically imputed to replace the missing end date of a dose administration record) will not be used to derive the last contact date.

## 2.2 Analysis sets

### Full Analysis Set (FAS)

The FAS comprises all subjects to whom study treatment has been assigned by randomization. According to the intent to treat principle, subjects will be analyzed according to the treatment and strata, to which they have been assigned to during the randomization procedure.

### Safety Set

The Safety Set includes all subjects who received at least one dose of study treatment. Subjects will be analyzed according to the study treatment received, either canakinumab and/or pembrolizumab, where treatment received is defined as the randomized treatment if the subject took at least one dose of that treatment or the first treatment received if the randomized treatment was never received.

### Pharmacokinetic analysis set (PAS)

The PAS consists of all subjects who received at least one dose of study drug and have at least one evaluable PK sample. The PAS will be defined for canakinumab and pembrolizumab separately.

**The canakinumab pharmacokinetic analysis set (PAS-canakinumab)** includes all subjects who provide at least one evaluable canakinumab PK concentration. For a concentration to be evaluable, subjects are required to:

- Receive at least one dose of canakinumab prior to sampling except C1D1 pre-dose sample

- Have pre-dose samples drawn prior to the 2nd dose of canakinumab
- Receive 200 mg of canakinumab prior to post-dose PK sampling
- It is collected (except for cycle 1 day 1) between 16 days (384 hours) and 26 days (624 hours) after the last 200 mg canakinumab dose administration

**The pembrolizumab pharmacokinetic analysis set (PAS-pembrolizumab)** includes all subjects who provide at least one evaluable pembrolizumab PK concentration. For a concentration to be evaluable, subjects are required to:

For pre-dose sample:

- It is collected before the next dose administration
- It is collected (except for cycle 1 day 1) between 16 days (384 hours) and 26 days (624 hours) after the last 200 mg pembrolizumab dose administration

For post-dose sample:

- Received 200 mg of pembrolizumab prior to post-dose PK sampling
- For end-of-infusion samples, have the sample collected within 2 hours post end of infusion

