8.5 Additional assessments

8.5.1 Pharmacokinetics

8.5.1.1 Pharmacokinetics (PK), immunogenicity (IG) and pharmacodynamic (PD) assessments

To evaluate canakinumab and pembrolizumab exposure and immunogenicity in this indication, and also to evaluate exposure of the proposed dosing regimen, sample collections for analysis of PK and ADA are currently planned for canakinumab and pembrolizumab when administered alone and in combination.

Blood samples will be taken by either direct venipuncture or an indwelling cannula inserted in a forearm vein. Samples are collected from the arm opposite from infusion site. If drug was administered via a central venous catheter, sample collection for PK/IG/PD should be from a different site.

For all PK/IG/PD analytes, the exact date and time of dosing, as well as the exact collection date and time of blood sampling must be recorded on the appropriate eCRF. All samples will be given a unique sample number and a dose reference ID.

If subjects experience an AE or SAE leading to discontinuation of the study treatment, an unscheduled PK and IG blood sample should be obtained as close as possible to the event occurrence. If anaphylactoid reactions occur after injection, two more canakinumab IG samples (at the time of the event and 8 weeks later) need to be taken. Refer to [Central Laboratory Manual] and flowchart for detailed PK, IG and PD collection for canakinumab, and PK, IG collection for pembrolizumab.

Timepoints of blood sample collection for canakinumab PK, IG and PD are outlined in Table 8-5.

Table 8-5 Blood collection schedule for canakinumab (s.c. injection, 200 mg Q3W) PK, IG and PD

Dose Reference Identification (ID)	PK sample number	IG sample number ^b	Total IL-1 β (PD) sample number ^b	Scheduled timepoints (hours)		
				Cycle	Day	Scheduled time (hours)
101	1	11	21	1	1	0 h / pre-dose ^a
101/102*	2	12	22	2	1	504 h post dose / 0 h pre-dose ^a
	3	13	23	EOT	NA	Anytime

Dose Reference Identification (ID)	PK sample number	IG sample number ^b	Total IL-1 β (PD) sample number ^b	Scheduled timepoints (hours)		
				Cycle	Day	Scheduled time (hours)
	4	14	24	safety follow-up 1 (26 days post-EOT)	NA	Anytime
	5	15	25	safety follow-up 3 (78 days post-EOT)	NA	Anytime
	6	16	26	safety follow-up 5 (130 days post-EOT)	NA	Anytime
	1001+ ^c	2001+ ^d	3001+ ^e	NA	NA	Unscheduled

* The first Dose Reference ID is for last dose received prior to the collection of the PK sample, while the second Dose Reference ID is for the current dose

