#### **PK concentrations**

Descriptive statistics (n, m (number of non-zero concentrations), arithmetic mean, CV% mean, SD, median, geometric mean, CV% geo-mean, minimum and maximum) for canakinumab concentration will be presented at each scheduled time point for the PAS-canakinumab.

Individual concentration-time profiles for canakinumab evaluable concentrations with median will be displayed graphically for PAS-canakinumab on the semi-log view. In addition, the mean (+/- SD) and geometric mean concentration-time profiles for canakinumab over time will be displayed graphically for PAS-canakinumab on the linear and semi-log view.

All individual plasma canakinumab concentration data will be listed by treatment using the FAS.

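### SAP 2.2 applies a window centred on the C2D1 pre-dose sample to every later canakinumab concentration, so at most one of the four samples after dose 2 can be evaluable

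*SAP*

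**What the plan says.** SAP 2.2 defines PAS-canakinumab through evaluable concentrations and lists four conditions under a single lead-in. The third is "Receive 200 mg of canakinumab prior to post-dose PK sampling". The fourth is "It is collected (except for cycle 1 day 1) between 16 days (384 hours) and 26 days (624 hours) after the last 200 mg canakinumab". Nothing divides the list into pre-dose and post-dose samples.

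The next paragraph defines PAS-pembrolizumab. The same window, "between 16 days (384 hours) and 26 days (624 hours) after the last 200 mg pembrolizumab dose administration", appears there under a sub-heading for pre-dose samples, and post-dose samples have a separate block without it.

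Protocol Table 8-5 schedules six canakinumab PK samples: C1D1 pre-dose, C2D1 pre-dose (timed at "504 h post dose / 0 h pre-dose"), EOT, and safety follow-ups 1, 3 and 5, which fall 26, 78 and 130 days after EOT. EOT and the follow-up samples may be drawn at any time of day or dosing interval.

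The term matters in SAP 2.8: "Individual concentration-time profiles for canakinumab evaluable concentrations with median will be displayed graphically". The descriptive statistics there carry no such limit; they are specified as "for canakinumab concentration will be presented at each scheduled time point for the PAS-canakinumab". Protocol 12.5.3 plans to show all concentration data for both drugs graphically against time, and SAP section 4 declares no change to protocol-specified analyses.

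**The concern.** The window suits one sample only, yet the text applies it to five of the six. No canakinumab sample is scheduled between C2D1 pre-dose and EOT. Apart from C2D1 itself, the post-dose sampling in the third condition can therefore only mean EOT, follow-up and unscheduled samples. If the fourth condition also governs those, the third adds nothing, because the fourth already counts from the last 200 mg dose. The list is then at odds with itself.

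Canakinumab PK is a stated secondary objective. The individual profiles are the planned plot that would show each subject's own course after dose 2. Programmed as written, they lose the late samples and, depending on when EOT falls, every sample after dose 2. That would also be an undeclared departure from protocol 12.5.3.

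**Working it through.** **Inputs**

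- Window: 384 to 624 h, or 16 to 26 days, after the last 200 mg dose (SAP 2.2).
- C2D1 pre-dose: nominal 504 h, drawn within 24 h before the dose (Table 8-5); dosing window ± 3 days (Table 8-1).
- EOT: at most 21 days after permanent discontinuation and before surgery (Table 8-1).
- Follow-ups 1 and 3: EOT + 26 and EOT + 78 days, each ± 7 days. Follow-up 5: EOT + 130 days, with + 14 days allowed (Tables 8-1 and 8-5).
- Surgery: 4 to 6 weeks, or 28 to 42 days, after dose 1 (protocol section 3).
- Canakinumab interruption: at most 1 week (protocol 6.5.1).

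**Step 1: what the window fits.** 16 × 24 = 384 h and 26 × 24 = 624 h, so the SAP's conversion is right. Midpoint: (384 + 624)/2 = 504 h. Half-width: (624 − 384)/2 = 120 h. With dose 2 given 18 to 24 days after dose 1 and the sample drawn up to a day earlier, the C2D1 sample lies at 17 to 24 days, wholly inside 16 to 26.

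**Step 2: the four samples after dose 2.** Let E be the number of days from the last canakinumab dose to EOT. If permanent discontinuation is counted from the last dose, E runs from 0 to 21.

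- EOT is at E, so it qualifies only if E ≥ 16.
- Follow-up 1 is at E + 19 to E + 33. It can qualify only if E + 19 ≤ 26, so E ≤ 7. At its nominal day, E + 26, it qualifies only if E = 0.
- Follow-up 3 is at E + 71 to E + 85, so 71 to 106 days. It never qualifies.
- Follow-up 5 is at E + 130 to E + 144, so 130 to 165 days. It never qualifies.

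| E (days) | EOT | Follow-up 1 | Follow-ups 3 and 5 | Maximum of 4 |
|---|---|---|---|---|
| 0–7 | no | possible | no | 1 |
| 8–15 | no | no | no | 0 |
| 16–21 | yes | no | no | 1 |

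EOT and follow-up 1 are at least 19 days apart and the window is 10 days wide, so both can never qualify. Varying E from 0 to 60 days leaves the maximum at 1.

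**Step 3: can EOT qualify in practice?** The earliest qualifying EOT, in days after dose 1, is the dose gap plus 16.

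- Dose 2 at 18 days: 18 + 16 = 34.
- Dose 2 at 21 days: 21 + 16 = 37.
- Dose 2 at 24 days: 24 + 16 = 40.
- Dose 2 at 28 days, after a one-week interruption: 28 + 16 = 44, which exceeds 42, so it can qualify only if surgery is later than 6 weeks.

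EOT must precede surgery at 28 to 42 days, so only the later part of that range leaves room. The documents do not say how often each case occurs.

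**Step 4: with the window limited to pre-dose samples.** All four samples after dose 2 could be evaluable, subject to the other conditions.

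**The case against.** The strongest reply is that this is a drafting slip with an obvious intent. The fourth condition matches the pembrolizumab pre-dose condition apart from the drug name. Its only exemption, C1D1, is itself a pre-dose sample. It does not fit the grammar of its lead-in, and the conditions before it already distinguish pre-dose from post-dose samples. A programmer who also reads protocol 12.5.3 might well limit it to pre-dose samples. All of this makes a lost sub-heading likely. It does not change what the SAP says, and the SAP is what gets programmed. The pembrolizumab sub-headings are present in the same section.

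A deliberate restriction is also conceivable: protocol 12.1.3 leaves the definition of an evaluable sample to the SAP, and no half-life or washout endpoint is stated. But it would make the third condition redundant, treat the two drugs differently without explanation, and conflict with protocol 12.5.3 while SAP section 4 declares no change.

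One qualification stands. In the combination arm one drug may continue alone in cycle 2, and EOT is set once all drugs have stopped. If canakinumab ended after dose 1, E could be about 21 + 21 = 42 days, so the upper limits of 106 and 165 days are not universal. The conclusions for follow-ups 3 and 5, and the maximum of one, are unaffected.

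The objection that the effect is small is right, and the grading reflects it.

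**Conclusion.** The rule is wrong as written, and the point is minor. Of six scheduled canakinumab samples, two (follow-ups 3 and 5) can never be evaluable. Of the four after dose 2, at most one can be, and none when EOT is 8 to 15 days after the last dose. The day ranges rest on counting discontinuation from the last canakinumab dose; the maximum of one does not depend on E staying within 21 days.

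The consequence is confined to the individual canakinumab profiles in SAP 2.8, if the rule is programmed literally. PAS membership does not change, because the C1D1 sample is exempt and one evaluable sample is enough. The FAS listing and the primary and safety results do not change. On the ordinary reading neither do the by-visit statistics and mean profiles, which carry no evaluability limit.

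**What to change.** In SAP 2.2, place the canakinumab 16-to-26-day condition under a pre-dose sub-heading, as for pembrolizumab, so that it covers only the C2D1 pre-dose sample. Treat EOT and follow-up samples as evaluable when 200 mg was given before sampling, and plot them in the individual profiles at actual time since the last dose. In SAP 2.8, add one sentence confirming that the by-visit statistics include the EOT and follow-up samples. This only closes off a second reading; no new evaluability limit should be added there.

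The cost is one sub-heading, one sentence and a small programming change. No extra data are needed, because protocol 8.5.1.1 already requires that "the exact date and time of dosing, as well as the exact collection date and time of blood sampling must be recorded". The change also brings the individual profiles back into line with protocol 12.5.3.

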### **Subject Classification:**

Subjects may be excluded from the analysis populations defined above based on the protocol deviations entered in the database and/or on specific subject classification rules defined in [Table 2-3](#).

**Table 2-3      Subject classification based on protocol deviations and non-PD criteria**

Analysis set	Protocol deviations leading to exclusion	Non protocol deviation leading to exclusion
FAS	No written informed consent	Not applicable
Safety Set	No written informed consent	No dose of any component of study treatment
PAS-canakinumab	No written informed consent	See definition of PAS-canakinumab
PAS-pembrolizumab	No written informed consent	See definition of PAS-pembrolizumab

### **Withdrawal of Informed Consent**

Any data collected in the clinical database after a subject withdraws informed consent from all further participation in the trial, will not be included in the analysis. The date on which a subject withdraws full consent is recorded in the eCRF.

Additional data for which there is a separate informed consent, e.g. PK, biomarker etc., collected in the clinical database without having obtained that consent will not be included in the analysis. These data will be excluded by the presence of the appropriate protocol deviation criterion.

## 2.2.1 Subgroup of interest

Due to small sample size for each arm, no formal subgroup analyses is planned. [REDACTED]

[REDACTED] More details can be found in [Section 2.10](#) and [Section 2.11](#).

## 2.3 Subject disposition, demographics and other baseline characteristics

The Full Analysis Set (FAS) and Safety Set will be used for all baseline and demographic summaries and listings unless otherwise specified. Summaries will be reported by treatment arm. In addition, listings will be reported by treatment arm. No inferential statistics will be provided.

### Enrollment status

The following summaries will be provided for the FAS in each of the three treatment arms:

1. Number (%) of subjects who were randomized
2. Number (%) of subjects who received at least one dose of study treatment after randomization

Number (%) of subjects screened will be summarized by country and center. In addition, the number (%) of subjects randomized will be summarized by country, center and treatment group.

For subjects who are screen failures, the reasons for not completing screening will be summarized based on “Screening Phase Disposition” eCRF.

### Basic demographic and background data

Demographic and other baseline data including disease characteristics will be summarized and listed by treatment arm. Categorical data (e.g. gender, age groups: <65 and  $\geq$  65 years, race, ethnicity, WHO performance status, smoking history) will be summarized by frequency counts and percentages; the number and percentage of subjects with missing data will be provided. Continuous data (e.g. age, weight, height, body mass index) will be summarized by descriptive statistics (e.g., N, mean, median, standard deviation, percentiles, minimum and maximum).

BMI ( $\text{kg}/\text{m}^2$ ) will be calculated as  $\text{weight}[\text{kg}] / (\text{height}[\text{m}]^2)$  using weight and height at baseline.

### Baseline stratification factors

The number (%) of subjects in each randomization stratum based on data obtained from the IRT system will be summarized overall and by treatment arm for the FAS. Discordances between the stratum recorded in IRT at the time of randomization and the actual stratum recorded in the clinical database through the data collected on eCRF will be cross-tabulated and listed.

## **Diagnosis and extent of cancer**

Summary statistics will be tabulated for diagnosis and extent of cancer. This analysis will include the following: primary site of cancer, predominant histology/cytology, additional histology/cytology, stage at initial diagnosis, time since initial diagnosis, stage at time of study entry and other relevant information if collected.

## **Medical history**

Relevant medical histories and current medical conditions at baseline will be summarized and listed by treatment arm. The summaries will be presented by primary system organ class (SOC), preferred term (PT) and treatment arm. Medical history and current medical conditions will be coded using the Medical Dictionary for Regulatory Activities (MedDRA) terminology. The MedDRA version used for reporting will be specified in the CSR and as a footnote in the applicable tables/listings.

## **Other**

All data collected at baseline (e.g., other informed consent than main study informed consent) will be listed.

## **Subject disposition**

The number (%) of randomized subjects included in the FAS will be presented by treatment arm. The number (%) of screened and not-randomized subjects and the reasons for screening failure will also be displayed. The number (%) of subjects in the FAS who are still on treatment, who discontinued the study phases and the reason for discontinuation will be presented overall and by treatment arm.

The following summaries will be provided (with % based on the total number of FAS subjects):

- Number (%) of subjects who were randomized (based on data from IRT system)
- Number (%) of subjects who were randomized but not treated (based on ‘DAR’ eCRF page not completed for any study treatment component)
- Primary reason for not being treated (based on “Treatment disposition” eCRF page)
- Number (%) of subjects who were treated (based on ‘DAR’ eCRF pages of each study treatment component completed with non-zero dose administered)
- Number (%) of subjects who are still on-treatment (based on the ‘Treatment disposition’ page not completed);
- Number (%) of subjects who discontinued the study treatment phase (based on the ‘Treatment disposition’ page)
- Primary reason for study treatment phase discontinuation (based on the ‘Treatment disposition’ page)
- Number (%) of patients who are still in the safety follow-up phase (based on presence of the ‘Treatment disposition’ page and absence of the ‘Study disposition’ page)

- Number (%) of patients who discontinued from safety follow-up phase (based on completion of ‘Study disposition’ page)
- Primary reasons for discontinuation from safety follow-up phase (based on discontinuation reasons entered under ‘Subject Status’ in the ‘Study discontinuation’ page).

### **Protocol deviations**

The number (%) of subjects in the FAS with any protocol deviation will be tabulated by deviation category (as specified in the edit-check specification) overall and by treatment arm for the FAS. All protocol deviations will be listed.

In addition to the pre-defined standard PD terms, Novartis has also defined 6 new protocol deviations and the corresponding relationship (health status related vs. site lockdown, patient concerns, etc.) to the COVID-19 pandemic in line with “FDA Guidance on Conduct of Clinical Trials of Medical Products during COVID-19 Public Health Emergency” ([March 2020](#)) and “Guidance on the management of clinical trials during the COVID-19 (coronavirus) pandemic” ([April 2020](#)) from EMA as listed below. Two additional study specific PDs are also defined to capture treatment delay/interruption and MPR Assessment missed due to COVID-19. The following deviations related to the COVID-19 pandemic will be summarized.

- Missing visits
- Changes in procedures and assessments
- Planned visits not done at sites
- Changes in drug supply method
- Treatment not given
- Patient discontinuation due to COVID-19 situation
- Treatment delayed/interrupted
- MPR Assessment missed due to COVID-19

A cross-tabulation of COVID-19 related PD vs. corresponding relationship will also be produced by treatment arm.

### **Analysis sets**

The number (%) of subjects in each analysis set will be summarized by treatment arm and randomization stratum. Reasons for exclusion of patients from analysis sets will be tabulated separately overall and by treatment arm.

## **2.4      Treatments (study treatment, rescue medication, concomitant therapies, compliance)**

### **2.4.1    Study treatment / compliance**

Duration of exposure, cumulative dose, dose intensity (DI) and relative dose intensity (RDI) will be summarized by treatment arm. The number (%) of subjects with interruptions, discontinuation and the corresponding reasons, will be summarized and listed.

The safety set will be used for all summaries and listings of study treatment.

### **Duration of exposure to study drug**

Duration of exposure to study drug (canakinumab and pembrolizumab) is defined as

Duration of exposure (days) = (last date of exposure to study drug) – (date of first administration of study drug) + 1

### **Duration of exposure to study treatment**

Duration of exposure to study treatment is the same as the duration of exposure to study drug for Canakinumab only and Pembrolizumab only treatment arms. For Canakinumab+Pembrolizumab arm, duration of exposure to study treatment is derived by taking into account the duration of exposure to each study drug:

Duration of exposure (days) = (last date of exposure to study treatment) – (date of first administration of study treatment) + 1

The duration includes the periods of temporary interruption except for the last one, a dose interruption occurring after the last date of exposure to study drug won't be considered. 'Date of first administration of study drug/treatment' and 'last date of exposure to study drug/treatment' are defined in [Section 2.1.3](#).

Duration of exposure to study drug/treatment will be summarized using descriptive statistics (mean, standard deviation etc).

